4.3 Exclusion criteria

A potential subject who meets any of the following criteria will be excluded from participation in this study:

- Primary tumour (T) clinical stage cT3-4
- Pre- or post-NST diagnosis of nodal disease including isolated tumour cells
- Concurrent LCIS of any type in either pre-NST biopsy or surgical specimen
- Patients without axillary ultrasound or FDG-PET/CT pre-NST
- History of breast cancer, DCIS or LCIS
- Synchronous contralateral breast cancer, DCIS or LCIS
- Synchronous M1 disease
- Carrier of gene mutation associated with increased risk of breast cancer, i.e. BRCA1, BRCA2, CHEK2, TP53 or PALB-2

4.4 Sample size calculation

Reported 5 year local and locoregional recurrence rates for patients with stage 2 and 3 disease (cT1-4N0-3) treated with NST, breast conserving surgery and radiotherapy who achieve pCR range from 0 to 3.5%, in which patients with DCIS (all reports) and even isolated tumour cells (one report, with highest reported LR of 3.5%(23)) were included in the pCR group.

As radiotherapy in primary breast cancer reduces recurrence with at least a factor 2.5, local recurrence at 5 year without radiotherapy could be in the range of 0-8.75% for pCR patients.(28)

Recently, 5-year local recurrence rates in NST patients treated with breast conserving surgery without radiotherapy were reported in a relatively large group of 110 pCR patients, with a very low recurrence rate of 1.8%. Notably, this concerned a group of cT1-4N0-3 patients, with >60% of patients being node-positive. Also, residual DCIS was included in the pCR group.(27)

As we will include only node negative patients with tumours <5 cm AND will exclude patients with residual DCIS, we may expect the recurrence rate to be on the lower side of the hypothesized range of 0-8.75%. For our statistical analysis, we have therefore used an **expected rate of local recurrence of 4%**.

A 5 year **local recurrence rate of less than 6% is deemed acceptable**, as studies have shown that the effect of RT on local recurrence is mainly achieved in the first 5 years following treatment(40), especially in TN and Her2 positive subtypes which will constitute the majority of our population.

Simulations were performed to calculate the sample size of a two stage single arm trial (including an interim analysis of futility), using the one sample log rank test. Assuming a 5 year follow up and a 5 year uniform accrual, assuming as well an exponential distribution for survival, we calculated that the expected number of events when 325 patients are included should be at most 6, under the null hypothesis. If less or equal events are observed at that time, the trial continues and **595 patients** in total are needed to achieve a power of >80% (an one-side alpha of 0.05). The expected number of events during the study are 35 to exclude a local recurrence risk at 5 years of 6% or more, if the actual local recurrence rate is 4%.

5. TREATMENT OF SUBJECTS

5.1 Investigational product/treatment

Not applicable

5.2 Use of co-intervention (if applicable)

Not applicable

5.3 Escape medication (if applicable)

Not applicable

6. METHODS

6.1 Study parameters/endpoints

6.1.1 Main study parameter/endpoint

The primary endpoint of the DESCARTES study is the local recurrence rate after 5 years.

6.1.2 Secondary study parameters/endpoints

- Local non-salvageable recurrence free survival (i.e. an in-breast recurrence that cannot be adequately cured with breast conserving surgery with RTx) after 5 years
- Quality of life at baseline and after 1 and 4 years after surgery
- Cancer worry at baseline and after 1 and 4 years after surgery
- Regional recurrence after 5 years
- Distant RFS after 5 and 10 years
- Disease-specific survival after 5 and 10 years
- OS after 5 and 10 years

6.2 Randomisation, blinding and treatment allocation

This is a prospective non-randomized clinical trial.

6.3 Study procedures

- Neoadjuvant systemic therapy

Patients included in the DESCARTES trial will receive neoadjuvant chemotherapy +/antiHER2 therapy according to national and local breast cancer guidelines.

- Surgery of breast and axilla

Breast conserving surgery should be performed. If studies show post-NST biopsies to be equally reliable in assessing pCR, these may substitute surgery following protocol amendment. Axillary surgery will consist of SLNB.

- Pathology examination

Breast and lymph node tissue will be assessed according to standard clinical practice. Pathologic complete response is defined by the absence of any residual tumour or DCIS cells, including isolated tumour cells. In case One-Step Nucleid Acid Amplification (OSNA) is used to determine status of sentinel node, only negative OSNA results will be accepted as N0.

- Inclusion and follow-up

Patients are not randomized. Patients will be followed for 10 years and assessed for local disease recurrence with yearly mammography and physical examination in the first 5 years. After five years the patient may be referred back to the breast cancer screening program. At 10 years, data on recurrence will be retrieved for all patients. If deemed necessary by the medical specialist assessing the patient, additional imaging and/or histopathology analysis may be performed. Axillary recurrences should be confirmed with pathology analysis. All lesions suspect for disease recurrence are discussed at multidisciplinary meetings, according to clinical practice guidelines. QoL will be evaluated with the PROMs including the EORTC QLQ-C30 and BR23. Additionally the Cancer Worry Scale, education level and 12-item Intolerance of uncertainty scale will be used to measure if anxiety is related to omission of radiotherapy may affect QoL.

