Patients will be followed yearly for a period of 5 years and at 10 years to assess localregional recurrence. Quality of life (QOL) is measured using the Patient Reported Outcome Measures (PROMs), which are integrated in standard care in the Antoni van Leeuwenhoek and other centers, and additional questionnaires containing measure not included in the standard PROMS set. The PROMs include the EORTC-QLQ-C30 and EORTC-QLQ-BR23. The 8-item Cancer Worry Scale will be used to measure if worry related to omission of radiotherapy may affect QOL. Two demographic variables (education level and tolerance for uncertainty) will be measured at baseline as these patient characteristics could be associated with quality of life and level

DESCARTES study

of experienced cancer worry and need to be considered in the analyses. The additional QOL questionnaires are provided simultaneously with the PROMs: the first are provided for baseline measurement, and the following are provided at 1 year and 4 years after surgery. See table 3 for an overview of the QOL measurements.

All recurrences should be confirmed with pathology analysis. All lesions suspect for disease recurrence are discussed at multidisciplinary meetings, according to clinical practice guidelines.

*Sentinel node biopsy may be performed before start of neoadjuvant systemic therapy

Figure 1. Descartes trial study design

	PROMs	Additional QOL questionnaires
Baseline	EORTC-QLQ-C30, EORTC- QLQ-BR23	Education level, 12-item Intolerance of uncertainty scale, Cancer Worry Scale
1 year after surgery	EORTC-QLQ-C30, EORTC- QLQ-BR23	Cancer Worry Scale
4 years after surgery	EORTC QLQ-C30	Cancer Worry Scale, EORTC-QLQ-BR23

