8. STATISTICAL ANALYSIS

8.1 Primary study parameter(s)

The primary endpoint of the study is the local recurrence rate, defined as recurrence in the ipsilateral breast. Any LR is considered as an event and is included in the analysis. Time to LR will be estimated by the Kaplan-Meier method and compared to the acceptable rate of 6% at 5 years by the one sample log rank test. Additionally an estimation of cumulative incidence of LR using death as a competing risk will be computed.

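### The planned 35 events and >80% power need follow-up of 5 to 10 years per patient, but no recurrence assessment or retrieval is scheduled between year 5 and year 10

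*Protocol*

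**What the plan says.** Section 3 sets the schedule: "Patients will be followed yearly for a period of 5 years and at 10 years to assess localregional recurrence". Section 6.3 gives the detail. Follow-up lasts 10 years, with mammography and physical examination yearly in the first five. Then: "After five years the patient may be referred back to the breast cancer screening program. At 10 years, data on recurrence will be retrieved". The year-10 retrieval covers everyone. The referral is optional, and no retrieval is named between years 5 and 10.

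Section 4.4 assumes 5 years of uniform accrual, 5 years of follow-up and exponential times. It plans 595 patients, one-sided alpha 0.05 and power above 80%, and states: "The expected number of events during the study are 35 to exclude a local recurrence risk at 5 years of 6% or more", on the premise that the true rate is 4%. Section 8.4 repeats the design and adds the futility look at 325 patients. It prints alpha as 0.5, which I read as a misprint for 0.05.

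Section 8.1 counts every local recurrence, with no time limit, and has time to recurrence "compared to the acceptable rate of 6% at 5 years by the one sample log rank test". It does not say when a patient's time at risk ends.

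**The concern.** The one-sample log-rank test compares observed recurrences with the number expected at the 6% rate over all the time at risk that is counted. It is valid only if both cover the same time. If the event count relies on time after year 5, recurrence status in that time has to be known at the analysis. The schedule does not provide for this: at a cut-off 5 years after the last inclusion, only the very first entrants have reached year 10.

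At stake is the primary claim that local recurrence without radiotherapy is below 6% at 5 years. Depending on how the gap is handled, the test may pass too easily, pass too rarely, or have less power than stated.

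**Working it through.** **Inputs.** From 4.4: N = 595; null rate 6% and expected rate 4% at 5 years; one-sided alpha 0.05; 5 years of uniform accrual, 5 years of follow-up, exponential times. From 4.4 and 8.4: futility look at 325 patients, continue with 6 or fewer events. My assumptions: no dropout, and the share of post-year-5 recurrences known at the analysis, since the protocol gives neither.

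**Hazards.** λ = −ln(1 − rate)/5. At 4%, λ = 0.00816 per year; at 6%, λ = 0.01238 per year.

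**Reproducing the 35 events.** With the cut-off 5 years after the last entry, follow-up is uniform on 5 to 10 years. Expected events = N × {1 − [exp(−5λ) − exp(−10λ)]/(5λ)}. At 4%: 595 × [1 − (0.96 − 0.9216)/0.04082] = 595 × 0.05933 = 35.3. This matches 35. Simulating the two-stage test gives power of 80–83%, depending on the variance form, which matches the stated >80%. The interim figures fit too: 325 entries at 119 per year take 2.73 years, so median follow-up is 16.4 months (stated: 16.2), with 5.4 events expected under the null (stated: at most 6).

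**Five years per patient instead.** 595 × 0.04 = 23.8 events. 595 × 0.06 = 35.7 is also close to 35, but 4.4 ties its 35 to a true rate of 4%, and a 5-year cut gives about 69% power, not >80%.

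**Share after year 5.** 35.3 − 23.8 = 11.5 events, or 33%. Ignoring events, patient-years are 595 × 5 = 2,975 in years 1–5 and 535.5 + 416.5 + 297.5 + 178.5 + 59.5 = 1,487.5 in years 6–10. The later years are 1,487.5/4,462.5 = 33% of the total.

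**Consequence by rule for ending time at risk.** Two-stage simulation, constant hazard, final statistic (O − E)/√E or (O − E)/√[(O + E)/2]. The ranges cover both forms and repeated runs of 10,000 to 40,000 trials.

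| Rule | Type I error (true 6%) | Events (true 4%) | Power (true 4%) |
|---|---|---|---|
| To cut-off, all late events known | 4–5% | 35.3 | 80–83% |
| To cut-off, 90% known | 6–8% | 34.2 | not meaningful: alpha exceeded |
| To cut-off, 75% known | 11–14% | 32.4 | as above |
| To cut-off, 50% known | 26–30% | 29.6 | as above |
| Late events count, event-free women censored at year 5; all late events reported | near 0 | 35.3 | 5–8% |
| Same, half of late events reported | below 0.5% | 29.6 | 28–32% |
| Everyone stops at year 5 | about 5% | 23.8 | about 69% |
| Wait for every patient's year 10 | 4–5% | 46.6 | about 87% |

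In the second to fourth rows, unknown recurrences are counted as event-free to the cut-off, so expected events accrue in full and observed events do not. In the fifth and sixth rows, late events enter without the event-free time that goes with them.

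**The case against.** The strongest objection is that the protocol does not fix any of these outcomes. It promises 10 years of follow-up, makes referral to screening optional, and does not bar sites from reporting recurrences found in usual care between years 5 and 10. The safety committee in 7.5 also monitors recurrences with no 5-year limit. Cut-off and censoring rules are commonly left to a statistical analysis plan, which is not at hand.

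Much of this stands. A reader might infer that late recurrences will be under-counted and that the error rate will therefore rise. The documents do not support that. It requires women of unknown status to be counted as event-free to the cut-off, and nothing says so. Another handling biases the test the other way, and two others keep the error at or below about 5%. The capture shares are my assumptions.

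The mismatch itself is not answered. A statistical analysis plan can choose a censoring rule, but it cannot supply recurrence status that sites were never asked to collect. The collection schedule belongs in the protocol, and the event count and power are the protocol's own figures.

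**Conclusion.** The point holds as an inconsistency between the sample size and the follow-up schedule. The 35 events and >80% power require time at risk up to 10 years, and about one third of the events (11.5 of 35.3) fall where no assessment or retrieval is scheduled before the analysis.

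The direction and size of the harm are conditional on the unstated rule for ending time at risk: type I error of about 6–8% or more if late recurrences are partly missed in counted time; power of roughly 5–32% if late events are counted one-sidedly; or correct error with about 24 events and 69% power if time stops at year 5. Waiting for all year-10 retrievals avoids these problems, with about 47 events and 87% power, but that is not the stated 35-event design.

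The figures rest on a constant hazard (as 4.4 assumes), no dropout, and a cut-off 5 years after the last inclusion, which I infer because it reproduces the 35 events.

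**What to change.** Preferred: in 6.3, add one recurrence-status retrieval for all patients at the primary analysis cut-off, 5 years after the last inclusion, using the procedure already planned for year 10. In 8.1, state that each patient's time at risk ends at the last date on which her recurrence status was ascertained, by the same rule whether or not she had an event. This keeps the 35-event design as calculated, to the extent that the retrieval is complete.

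Alternative: limit the primary test to 5 years per patient, amend the statement in 8.1 that every local recurrence counts so that it matches, and restate 4.4 and 8.4 as about 24 events and about 69% power.

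The preferred route costs one extra round of data retrieval and a few sentences, with no added patients, visits or imaging. The alternative costs a less favourable stated power.

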6.4 Withdrawal of individual subjects

Subjects can leave the study at any time for any reason if they wish to do so without any consequences. The investigator can decide to withdraw a subject from the study for urgent medical reasons.

6.4.1 Specific criteria for withdrawal (if applicable)

Not applicable.

6.5 Replacement of individual subjects after withdrawal

Not applicable.

6.6 Follow-up of subjects withdrawn from treatment

Not applicable.

6.7 Premature termination of the study

If the interim analysis for futility shows a higher than acceptable local recurrence rate, the study will be terminated. See statistics for detailed information.

7. SAFETY REPORTING

7.1 Temporary halt for reasons of subject safety

In accordance to section 10, subsection 4, of the WMO, the sponsor will suspend the study if there is sufficient ground that continuation of the study will jeopardise subject health or safety. The sponsor will notify the accredited METC without undue delay of a temporary halt including the reason for such an action. The study will be suspended pending a further positive decision by the accredited METC. The investigator will take care that all subjects are kept informed.

7.2 AEs, SAEs and SUSARs

7.2.2 Serious adverse events (SAEs)

A serious adverse event is any untoward medical occurrence or effect that

- results in death;
- is life threatening (at the time of the event);
- requires hospitalisation or prolongation of existing inpatients' hospitalisation;
- results in persistent or significant disability or incapacity; or
- any other important medical event that did not result in any of the outcomes listed above due to medical or surgical intervention but could have been based upon appropriate judgement by the investigator.

An elective hospital admission will not be considered as a serious adverse event.

All serious adverse events that occur within 90 days of omission of radiotherapyconsidered by the investigator to be related to study treatment, must be medically well documented and reported to the NKI Data Center within 24 hours or, at the latest, on the following working day.

The report must be sent by email ([contact]) to the Antoni van Leeuwenhoek Data Centre. The Data Centre can also be contacted by telephone ([name]) between 09.00 and 17.00 hours (GM+1) Monday to Friday. The sponsor will not report the SAEs through the web portal ToetsingOnline. All SAEs will be reported to the accredited METC that approved the protocol, within 7 days of first knowledge for SAEs that result in death or are life threatening followed by a period of maximum of 8 days to complete the initial preliminary report. All other SAEs will be reported within a period of maximum 15 days after the sponsor has first knowledge of the serious adverse events.

7.5 Safety Committee

A data safety committee will be established to monitor the number and nature of any recurrences that may occur. The data safety committee will consist of a surgical oncologist, radiation oncologist, pathologist and statistician.

8. STATISTICAL ANALYSIS

8.1 Primary study parameter(s)

The primary endpoint of the study is the local recurrence rate, defined as recurrence in the ipsilateral breast. Any LR is considered as an event and is included in the analysis. Time to LR will be estimated by the Kaplan-Meier method and compared to the acceptable rate of 6% at 5 years by the one sample log rank test. Additionally an estimation of cumulative incidence of LR using death as a competing risk will be computed.

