1. INTRODUCTION AND RATIONALE

NST is increasingly used in breast cancer treatment(1), resulting in tumour downsizing and increase in breast conserving surgery(BCS) rates without compromising local recurrence or overall survival.(2-6) The extent of tumour downsizing is largely dependent on breast cancer molecular subtypes with highest pCR rates in triple negative(TN) and HER2+ subtypes (40-88%) and pCR rates of 10-15% in HR+/HER2- breast cancer.(7-14)

De-escalating locoregional treatment following NST cannot be achieved by omitting surgery, since biopsies or MRI do not accurately assess pCR. (15-17). Adjuvant whole breast irradiation however may be de-escalated in pCR patients who do not have an indication for regional irradiation.(18)

In this patient group, risk of distant and local failure is low. Mamounas first reported retrospectively on cT1-3N0-2 patients treated with NST in two major clinical trials conducted from 1988 to 1993 and from 1995 to 2000. Only 10-year results on local recurrence were reported. In 225 clinically node-negative patients with pCR, local recurrence was 5.2 and 6.9% for patients >50 and <50 years respectively.(19) Notably, pCR definition included patients with residual in situ disease and axillary lymph node status was defined by palpation only. As the large majority of local recurrences occur within 5 years from treatment, especially in Her2 positive and triple-negative breast cancer, the reported 10-year recurrences will have included new primary cancers.(20) However, this overview confirmed that the absence of pCR was the most important predictor for locoregional recurrence with a hazard ratio of 2.77.(19)

Recent studies including up-to-date systemic treatments and pre-NST staging with MRI and axillary ultrasound report considerably lower 5 year recurrence rates, as shown in Table 1. All studies include patients with stage I-III disease and include residual DCIS in pCR definition. Samples sizes for pCR patients vary between 157 and 426, with **local** recurrence rates between 1.0-3.5%, with isolated tumour cells considered pCR in the highest reported recurrence. **Locoregional** recurrence rates in pCR patients range from 0.0%-3.2%.(21-23) Swisher et al report recurrence rates per molecular subtype, with lowest rates in hormone receptor positive breast cancer.(22) Notably, 61% of patients in this cohort presented with node-positive disease, but LRR was not specified for cN0 versus cN+ patients.(22)

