2. OBJECTIVES

Primary Objective:

To show that omitting radiotherapy in patients with a pathologic complete response to NST results in a 5-year local control rate of >94%.

Secondary Objective:

To show that omitting radiotherapy in patients with a pathologic complete response to NST results in good quality of life without compromising cancer worry levels.

To assess the 5- and 10-year local control rate, distant- and regional metastasis free survival and local non salvageable recurrence free survival.

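### The primary log-rank test has no 5-year cut and the design figures rely on events after year 5, so its 5% level for the 5-year claim depends on a constant hazard

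*Protocol*

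**What the plan says.** Section 2 sets the objective: omitting radiotherapy "results in a 5-year local control rate of >94" per cent. Section 6.1.1 agrees: "The primary endpoint of the DESCARTES study is the local recurrence rate after 5 years".

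Section 8.1 says of the primary analysis "Any LR is considered as an event and is included in the analysis", and that time to local recurrence is "compared to the acceptable rate of 6% at 5 years by the one sample log rank test". It gives no time limit for events or person-time and does not name the null curve.

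Section 4.4 describes the design simulations: "Assuming a 5 year follow up and a 5 year uniform accrual, assuming as well an exponential distribution for survival". With 595 patients, power is above 80% at a one-sided level of 0.05. On events it says "The expected number of events during the study are 35 to exclude a local recurrence risk at 5 years of 6% or more", and it ties this count to an actual rate of 4%. Section 8.4 puts a futility look at 325 patients with a median follow-up of at least 16.2 months; the trial continues if there are at most 6 events.

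On timing, section 1 argues "As the large majority of local recurrences occur within 5 years from treatment, especially in Her2 positive and triple-negative breast cancer", and section 4.4 refers to an effect of radiotherapy in the first 5 years, "especially in TN and Her2 positive subtypes which will constitute the majority of our population". Sections 3 and 6.3 plan yearly assessment to year 5 and data retrieval at 10 years.

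**The concern.** A one-sample log-rank test compares all observed events with all events expected under the null curve, over all person-time that enters the analysis. If patients contribute time beyond year 5, the test is no longer about the 5-year rate alone. It tests whether the whole curve lies below the null curve, and the part after year 5 is an extrapolation of the 6% limit.

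If the real hazard drops after year 5 while the null hazard stays constant, the expected count grows faster than the observed count. The statistic then moves towards success even when the 5-year rate sits exactly at the limit. In a single-arm trial, that error would declare omission of radiotherapy acceptable when the protocol's own criterion is not met.

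**Working it through.** **Inputs.** Null rate 6% and alternative 4% at 5 years, N = 595, 5-year uniform accrual, 5-year follow-up, exponential times, one-sided level 0.05, and stopping if more than 6 events have occurred when patient 325 enters (sections 4.4 and 8.4). No dropout is stated, so none is assumed.

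**Hazards.** h = −ln(1 − p)/5, so h0 = −ln(0.94)/5 = 0.01238 per year and h1 = −ln(0.96)/5 = 0.00816 per year.

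**Accrual check.** 595/5 = 119 patients per year. Patient 325 enters at 325/119 = 2.73 years (32.8 months), so median follow-up is 32.8/2 = 16.4 months, against 16.2 stated. Expected null events at that time are 5.4, against at most 6 stated. The accrual model is therefore the protocol's.

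**Reproducing the 35 events.** With follow-up uniform on 5 to 10 years, expected events = N × [1 − (e^(−5h) − e^(−10h))/(5h)].
- At 4%: 595 × [1 − (0.9600 − 0.9216)/0.04082] = 35.3. This matches 35.
- At 6%: 595 × [1 − (0.9400 − 0.8836)/0.06188] = 52.65.

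Simulated power at 4%, rejecting when (O − E)/√E < −1.645, is 85% without the futility look and 80% with it. This matches the stated power.

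**Other follow-up readings.**
- Cut at 5 years: 595 × 0.04 = 23.8 events at 4%; power 72% without and 69% with futility.
- Follow-up of 0 to 5 years: 12.0 events at 4%.

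Neither matches.

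**Share of the planned information after year 5.** Null events by year 5 are 595 × 0.06 = 35.7, which leaves 52.65 − 35.70 = 16.95 later. The null 10-year rate is 1 − 0.94² = 11.64%, so the constant-hazard null places 6/11.64 = 52% of 10-year recurrences in the first 5 years.

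**False success at a true 5-year rate of exactly 6%** (uncut test, N = 595, futility look included). The multiplier is the hazard after year 5 relative to the earlier hazard. The last column puts 75% of the 5-year hazard in years 0 to 3.

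| Multiplier | Flat hazard to year 5 | Early-clustered hazard |
|---|---|---|
| 1 | 4.0% | 3.7% |
| 0.75 | 11.7% | 9.5% |
| 0.5 | 26.6% | 21.1% |
| 0.25 | 45.0% | 34.3% |

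If the large majority by year 5 means two-thirds, three-quarters or four-fifths of 10-year recurrences, the 10-year rates are 9.0%, 8.0% and 7.5% and the multipliers are 0.52, 0.35 and 0.26. False success is then 25%, 38% or 44% (early-clustered: 19%, 29% or 34%, because futility stops more trials).

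At a true rate of 7%, multipliers 0.75, 0.5 and 0.25 give 1%, 5% and 15%. With a 5-year cut, the figures are 4 to 5% at a true 6% and about 0.5% at 7%, whatever happens after year 5.

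**Opposite direction.** If the later hazard were 1.5 times the earlier one, the level would fall to 0.3 to 0.4%, and power at a 5-year rate of 4% would drop to 52 to 55%.

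**The case against.** **Analysis window left to the SAP.** A censoring rule and a reference curve may reasonably be left to an SAP, which is not shown. That disposes of a complaint about missing detail. It does not help the figures that the protocol does fix: an SAP that added a 5-year cut would protect the level and leave the events and power in sections 4.4 and 8.4 wrong.

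**No scheduled assessment between years 5 and 10.** If the final analysis comes 5 years after the last entry, much of the later person-time may not have been collected, and patients would in effect be censored near year 5. The level then holds and the problem becomes overstated power, about 69% against more than 80%. This stands as an alternative reading, and it still requires a correction.

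**The 35 events could be null events.** 595 × 6% = 35.7, so 35 could be the null count under a 5-year cut, and section 8.4 gives the 35 without mentioning 4%. Section 4.4 does tie the count to an actual rate of 4%, however, and this reading does not bring power above 80%.

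**The protocol gives no hazard after year 5.** This stands. The sentence in section 1 is background and does not describe patients without radiotherapy; section 4.4 speaks of when radiotherapy acts. New primaries in the same breast, if counted as local recurrence, would make the drop smaller. The multipliers therefore show a range and are not estimates.

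**Conclusion.** The concern holds, and the protocol needs correcting on either reading. Without a cut, the only reading that reproduces the design figures, the stated 5% level applies to the 5-year claim only if the average hazard after year 5 matches the constant-hazard null. The protocol's own premise points to a lower late hazard and so to too many false successes: about 12% for a mild drop and 27 to 45% for larger ones, at a true rate of 6%. With a cut, the level is sound, but the expected events are about 24, not 35, and power is about 69%, not above 80%.

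The event counts and power follow from the protocol's own inputs. The null curve and the 5 to 10 years of follow-up are inferred from sections 4.4 and 8.4, and the sizes of the inflation rest on assumed multipliers and no dropout. Because this test decides whether omission is called acceptable, the point should be settled before the primary analysis.

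**What to change.** - **Section 8.1:** state that the primary one-sample log-rank test uses observed and expected events up to 5 years per patient only, and name the null curve. Keep later data for the 10-year estimates. Requiring the one-sided 95% upper limit of the 5-year Kaplan-Meier rate to lie below 6% is a similar but not identical option. Its exact binomial counterpart with complete data and no futility look succeeds at 25 or fewer events, with level 3.4% and power 65%.
- **Sections 4.4 and 8.4:** restate the figures for 595 patients under the cut: about 24 events expected at 4%, success at 26 or fewer events, and power of about 69% with the futility look (72% without).

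The cost is text changes and lower stated power; no visits are added. Keeping 80% power under the cut would take about 860 patients with the present futility look, or roughly 775 to 800 without it. The latter is a range because the success limit is a whole number of events, so power moves in steps.
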